10.3 Rationale for Efficacy Endpoints

1) mRSS

mRSS is used internationally to assess severity of SSc^{13), 14)}. Moreover, mRSS is generally considered to be correlated with visceral involvement, etc. and change over a relatively short period of time by receiving treatment, etc. Therefore, change from baseline in mRSS at Week 24 has been selected as primary endpoint to evaluate the efficacy of this drug on SSc. Since SSc has a chronic course, change from baseline in mRSS at Week 52 has been also selected as an efficacy endpoint to discuss the clinical significance of this drug.

2) Respiratory Function Test

FVC in respiratory function tests has been shown to be a useful indicator for predicting vital prognosis in interstitial lung disease associated with SSc¹⁵⁾. %FVC and %DLco are useful parameters for screening pulmonary hypertension associated with SSc¹⁶⁾. Therefore, this test has been selected to evaluate the efficacy of this drug on lung lesion in an exploratory manner and to ensure the safety of participants.

3) Chest HRCT

Interstitial lung disease in SSc patients has been reported to be detected 50% to 60% by HRCT¹⁷⁾. Interstitial lung disease is the most common cause of death in SSc patients¹⁸⁾. Interstitial lung disease often occurs from the early stage of SSc, and therefore, it is useful to predict prognosis and determine whether the treatment is feasible for the patient. Moreover, the guidelines recommend to predict the risk of progression to end-stage pulmonary disease and determine whether the treatment is feasible for the patient by the fibrotic finding in HRCT and the extent of the lesion or of the entire lesion in conjunction with FVC-predicted values in respiratory function tests⁷⁾. Based on the above, this test has been selected to evaluate the efficacy of this drug on lung lesion in an exploratory manner and to ensure the safety of participants.

4) Severity Classification of Lung Lesion

The Guidelines for Diagnostic Criteria, Severity Classification and Clinical Practice of Systemic Sclerosis recommend to predict the risk of progression to end-stage pulmonary disease and determine whether the treatment is feasible for the patient by the fibrotic finding in HRCT, the extent of the lesion or of the entire lesion and FVC predictive value in respiratory function tests⁷⁾. This parameter has been selected to evaluate the efficacy of this drug on lung lesion in an exploratory manner and to ensure the safety of participants.

5) ACR-CRISS

ACR-CRISS is a composite response index for clinical trials in early diffuse cutaneous SSc¹⁹⁾, which is generally used in clinical trials in SSc patients. This index has been selected to evaluate the efficacy of this drug on SSc in an exploratory manner.

6) The number of digital ulcers

Ulcers of the fingers and toes are complications of vascular disorder, one of the conditions of SSc, which occur frequently (35-60%) and arise from the early stage of the disease; therefore, they are considered to reflect the condition of SSc. Moreover, the ulcers are often refractory and recurrent, which is directly related to participants' activities of daily living (ADL) and decreased QOL. Accordingly, this parameter has been selected to evaluate the efficacy of this drug on SSc in an exploratory manner.

7) HAQ-DI

HAQ is a convenient self-administered questionnaire assessing physical function for activities of daily living. It was originally developed to evaluate the effect of rheumatoid arthritis on activities of daily living; however, it has been reported that HAQ-DI correlates with the degree of skin thickening, cardiac involvement, renal involvement, etc., also in SSc²⁰⁾. Moreover, along with mRSS, it is a widely used standard method to evaluate SSc. Based on the above, HAQ-DI has been selected to evaluate the efficacy of this drug on SSc in an exploratory manner.

8) FACIT-Fatigue

FACIT-Fatigue is a health-related quality of life that assesses fatigue and its impact on daily activities and functions in chronic diseases. Shortness of breath and fatigue occur in interstitial lung disease and pulmonary hypertension associated with SSc. FACIT-Fatigue has been proven to be reliable and useful in various diseases including SSc¹⁰⁾. Thus, FACIT-Fatigue has been selected to evaluate the effects of this drug on fatigue and on daily living and functions in SSc, a chronic disease, in an exploratory manner.

9) FSSG

FSSG is a useful questionnaire to objectively assess the symptoms of Japanese participants with gastroesophageal reflux disease¹¹⁾. In SSc, esophageal involvement is complicated at a high rate from the early stage of the disease, and 80% to 90% of SSc patients have reflux esophagitis¹⁾. Esophageal involvements are also associated with the extent and duration of thickening¹⁾. Based on the above, FSSG has been selected to evaluate the efficacy of this drug on reflux esophagitis in SSc patients in an exploratory manner.

10) Global improvement rating (PtGA, PGA)

Global improvement rating is a widely used method to assess disease activity in clinical trials such as

in rheumatoid arthritis. This rating has been selected to evaluate the efficacy of this drug on SSc in an exploratory manner.

11. Safety Evaluation

11.1 Assessments for Safety Evaluations

- 1) Adverse events
 - a) Symptoms and signs
 - b) Abnormal laboratory test values
 - c) Abnormal vital signs
 - d) Abnormal electrocardiograms
- 2) Laboratory test values
- 3) Vital signs
- 4) Electrocardiograms
- 5) Echocardiography

11.2 Definition of Adverse Events

- 1) Adverse events (AEs)

An AE in the study will be defined as any undesirable or unexpected sign, symptom, disease, or aggravation of an existing condition occurring in a participant who is given an IP on or after the time of informed consent regardless of whether there is a causal relationship to the IP. The aggravation of diseases or symptoms that have occurred before the time of informed consent are also considered an AE.

The following events are not considered AE:

- Events for which medical treatment had been scheduled before the time of informed consent
- Aggravation of primary disease

- 2) Serious adverse events (SAEs)

- a) Results in death
- b) Is life-threatening
- c) Requires or prolongs inpatient hospitalization*

*Excluding the following events;

- Any hospitalization that had been scheduled before the time of informed consent (e.g., hospitalization for surgeries and detailed examinations)
- Any hospitalization for examinations without any treatment (including bed rest treatment).

- d) Results in persistent or significant disability/incapacity
- e) Is a congenital anomaly/birth defect
- f) Is another medically important condition*

*An important medical event that may not be immediately life-threatening or does not result in death or hospitalization but may jeopardize the safety of the patient or may require treatments to prevent one of the other outcomes listed in a) to e) above.

e.g., bronchospasm requiring intensive care at an emergency room, blood dyscrasias or convulsions not leading to hospitalization, drug dependence, or drug abuse

- 3) Adverse events of special interest (AESIs)

AESIs in this study are defined as the following treatment-emergent events:

- a) AEs requiring discontinuation of study treatment

- b) Injection-related reactions (including local and systemic injection site reactions)
Injection-related reactions are defined as AEs which develop within 24 hours after administration of IP.
- c) Asthma
- d) Atopic dermatitis
- e) Skin symptoms with edematous erythema or scales
- f) Skin infections
- g) Non-skin infections
- h) Suspected infection of infectious pathogen from the IP

• Rationale for selection

b), c), d), f), and g)	These events should be monitored carefully because of being included in “important potential risks” in nemolizumab.
e)	These are events of interest closely monitored by the sponsor based on the results of clinical studies of nemolizumab in patients with atopic dermatitis
h)	The event should be carefully investigated in biological products in general.

11.3 Definitions of Safety Endpoints

1) Adverse events

a) Symptoms and signs

The investigator or subinvestigator will assess symptoms and signs in participants after the time of informed consent through the time of physical examination on the day of follow-up visit based on interview results and complaints from participants.

b) Abnormal laboratory test values

The investigator or subinvestigator will treat laboratory test results collected after the time of informed consent through the day of follow-up visit as AEs if the results meet any of the following criteria:

- i. Accompanied with clinical symptoms
- ii. Resulted in any change of study treatment (e.g., interruption or discontinuation of the IP).
- iii. Resulted in medical treatment (including change of concomitant medications/therapies).
- iv. Considered clinically significant by the investigator or subinvestigator.
- v. Total bilirubin is >2-fold the upper limit of the reference value, and ALT or AST is >3-fold the upper limit of the reference value
- vi. ALT or AST is >3-fold the upper limit of the reference value with clinical jaundice

Individual abnormal changes in laboratory test findings will be reported as individual AEs in principle. However, a single abnormal laboratory test finding or two or more abnormal laboratory test findings that are related to each other may be reported collectively as a single event under a single diagnosis if it is considered appropriate by the investigator or sub-investigator. If individual abnormal changes in laboratory test findings are regarded by the investigator or subinvestigator as manifestations of a symptom or a sign reported as an AE, the changes may be reported collectively with the AE of the symptom or sign.

Laboratory values may change depending on interindividual factors, such as sex, age, and lifestyle, and intraindividual factors, such as diurnal fluctuation, diet, exercise, body positioning, and sexual cycle. Therefore, the investigator or subinvestigator will determine whether the change in each laboratory test findings is a physiological change or an abnormal change after sufficiently taking into

consideration the demographics of each participant, such as the underlying disease and complication, baseline values, and the changes specific to each participant who have any periodic laboratory test before study participation.

c) Abnormal vital signs

The investigator or subinvestigator will treat measurement results collected after the time of informed consent through the day of follow-up visit as AEs if the results meet any of the following criteria:

- i. Accompanied with clinical symptoms
- ii. Resulted in any change of study treatment (e.g., interruption or discontinuation of the IP).
- iii. Resulted in medical treatment (including change of concomitant medications/therapies).
- iv. Considered clinically significant by the investigator or subinvestigator.

d) Abnormal electrocardiograms

The investigator or subinvestigator will assess AEs based on the results collected after the time of informed consent through the day of follow-up visit

e) Echocardiography

Echocardiographic images will be assessed for cardiac morphology, cardiac motion and blood flow during cardiac contraction and relaxation, and other parameters. The investigator or subinvestigator will record the presence or absence of abnormalities in the source documents.

11.4 Review and reporting of adverse events

The investigator or subinvestigator will assess the items shown in [Table 11-1](#) regarding AEs occurring from after obtaining informed consent to the day of follow-up visit and fill the necessary information in the case report forms (CRFs).

The investigator or subinvestigator will report the SAEs according to [Section 11.5](#) and the AESIs according to [Section 11.6](#) to the sponsor. The investigator or subinvestigator will promptly report the other AEs to the sponsor.

Table 11-1 Assessments for adverse events

Assessments	Details of assessment	
Name of adverse event	Disease name/symptom, classification of the site of occurrence of adverse events	
Onset date	Classification of onset date, Onset date	
Action on investigational product	Treatment discontinuation, Treatment interruption, Dose reduction, No dose change, Not applicable, Unknown	
Treatment for the event	Presence or absence of treatment	
Outcomes and Date of outcome/Date of outcome obtained	Recovered/Resolved, Recovering/Resolving, Not Recovered/Not Resolved, Recovered/Resolved with sequelae, Death, and Unknown End date of AE, whether the AE is ongoing or not	
Severity	Mild	Transient, requiring minimal treatment and not interfering with daily life
	Moderate	Specified treatments relieve symptoms and do not result in permanent or significant disability but interfere with daily life
	Severe	Significant effect on advanced clinical condition or requiring intensive care or no longer allowing daily life.
Seriousness	Serious/Non-serious	
Definition of serious adverse events in Section 13.2	1. Results in death	
	2. Life-threatening	
	3. Requires or prolongs inpatient hospitalization	
	4. Results in persistent or significant disability/incapacity	
	5. Is a congenital anomaly/birth defect	
	6. Is another medically important condition	
Causal relationship with investigational product	Causality classification (according to the following causality classification), and rationale	
Causality classification*	Not related	Causal relationship is unlikely because the adverse event has no plausible temporal relationship to administration of IP, or the event can be explained by another factor. The rationale for no causal relationship is required to be described.
	Related	Causal relationship is presumed because there is a plausible temporal relationship between the onset of the adverse event and administration of investigational drug, and the event cannot be readily explained by another factor. The rationale for the causal relationship should be described if it is necessary to be explained.

*The following guidance can be taken into consideration on causality assessment: resolution of the event after discontinuation of IP; recurrence after restarting of IP; established causal relationship with IP or similar drugs; no confounding risk factors; consistency with the amount and duration of exposure to IP; almost clearly explainable involvement of the IP based on the correct past medical history; no reasonable possibility of causal relationship with concomitant therapy, etc.

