17.3.3 Safety Analysis

The following variables will be summarized on the safety analysis set:

1) Adverse events

The following data will be collected and tabulated for AEs and separately for the treatment-related AEs.

- a) The number of participants included in the safety analysis set, and the number of participants with, and the number of occurrences of AEs, AEs by severity (mild, moderate, and severe), SAEs (total, fatal, and non-fatal), and AESIs will be calculated.
- b) The number of participants with AEs will be calculated by SOC and PT using MedDRA/J.
- c) For AESIs, the number of participants with AESIs, the number of participants with AESIs by PT will be calculated by the category.

2) Laboratory test values

- a) Laboratory test values throughout the treatment period

For the continuous variables, summary statistics will be calculated by laboratory parameter and time point. For the categorical variables, the number of participants will be calculated by category. The percentage of participants will be calculated using the number of observed participants at each time point.

- b) Changes in individual participants during the treatment period

A spaghetti plot will be created for each participant using individual test values by laboratory parameter of continuous variables.

3) Vital signs, physical findings, and other assessments related to safety

- a) Vital signs, electrocardiogram and echocardiography throughout the study period

For the continuous variables, summary statistics will be calculated by vital sign, electrocardiogram parameter, and echocardiography parameter. For the categorical variables, the number and percentage of participants will be calculated by category. The percentage of participants will be calculated using the number of observed participants at each time point.

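### The two causality rows in Table 11-1 overlap and leave mixed-cause events unclassified, so treatment-related AE counts and SAE causality can be inconsistent and understated

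*Combined protocol and SAP*

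**What the plan says.** Table 11-1 in section 11.4 has two causality classes and no intermediate one.

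- *Not related*: a relationship is judged unlikely where the event "has no plausible temporal relationship to administration of IP, or the event can be explained by another factor". The same row adds: "The rationale for no causal relationship is required to be described".
- *Related*: a relationship is presumed when the timing is plausible "and the event cannot be readily explained by another factor".
- The footnote to the classification begins: "The following guidance can be taken into consideration on causality assessment: resolution of the event after discontinuation of IP; recurrence after restarting of IP". It goes on to known effects of the product or similar drugs, absence of confounding risk factors, consistency with exposure, and absence of a plausible role for concomitant therapy.

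The wording is the same in all three protocol versions in the combined document.

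The label is used in two places. Section 17.3.3 1) states: "The following data will be collected and tabulated for AEs and separately for the treatment-related AEs". Section 11.5 lists causal relationship among the SAE information to be updated with the sponsor. Section 19.3 treats causality entered only in the CRF as original data.

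Section 11.2 makes asthma, atopic dermatitis, skin infections and non-skin infections AESIs, whatever their causality. The reason given is "These events should be monitored carefully because of being included in" the list of important potential risks of nemolizumab.

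**The concern.** A binary classification should put every event in exactly one class. Here one row turns on whether another factor can explain the event, and the other on whether it can *readily* do so. Events between the two thresholds belong to both classes, so two investigators could label the same event oppositely and both comply.

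The rows also do not mention contributory causation. An infection in a participant taking the low-dose oral steroid allowed by section 8.4.1 may have two contributors. The table does not say which class it belongs to, and the existence of another explanation is by itself a ground for *Not related*.

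Safety is a stated objective of a single-arm study, and treatment-related AEs are a separate planned output. A short treatment-related list for infections could reflect how the rows were read as much as what the drug did.

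**Working it through.** The documents give no AE rate and no figure that depends on causality, so there is nothing to reproduce. The main check is logical. The arithmetic after it is only illustrative.

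**Step 1. The rows as conditions.** Take timing as plausible or not, and the other explanation as none, possible but not ready, or ready.

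| Timing | Other explanation | Meets *Related* | Meets *Not related* |
|---|---|---|---|
| Implausible | Any | No | Yes |
| Plausible | None | Yes | No |
| Plausible | Possible, not ready | Yes | Yes |
| Plausible | Ready | No | Yes |

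The third line is double-classed. This needs no numerical assumption. Whether the drug may also have contributed is not a condition in either row and enters only through the optional footnote.

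**Step 2. How much timing separates events.** Section 8.3 gives dosing every 4 weeks and a half-life of 12.6 to 14.6 days. The fraction of a dose left at 28 days is 2^(−28/12.6) = 0.21 to 2^(−28/14.6) = 0.26. Drug is present between doses, so most on-treatment events will have plausible timing. The label then rests largely on the other explanation, which is where the rows disagree.

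**Step 3. Effect on counts of participants.** Inputs: n = 8 (section 17.4.1); p = 0.3, the assumed share of participants with an infection; q, the assumed share of those classed *Not related* because of another factor. Expected related participants = 8 × p × (1 − q). Chance of at least one = 1 − (1 − p(1 − q))^8.

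| q | Expected related | Chance of at least one |
|---|---|---|
| 0 (same as all-causality) | 2.4 | 0.94 |
| 0.25 | 1.8 | 0.87 |
| 0.5 | 1.2 | 0.73 |
| 0.75 | 0.6 | 0.46 |
| 0.9 | 0.24 | 0.22 |
| 1 | 0 | 0 |

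The chance of at least one in the all-causality table depends on p alone: 0.57 at p = 0.1, 0.83 at p = 0.2, 0.94 at p = 0.3 and 0.996 at p = 0.5.

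**Step 4. Effect on counts of events.** Assume 8 participant-years, a background of 1 infection per participant-year and Poisson counts. At q = 0.8, expected related infections are 8 × 0.2 = 1.6, 16 × 0.2 = 3.2 and 24 × 0.2 = 4.8 at rate ratios 1, 2 and 3. At rate ratio 2, the chance that the related table shows none is exp(−3.2) = 0.04 at q = 0.8, exp(−0.8) = 0.45 at q = 0.95, and 1 at q = 1.

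**Step 5. The limit set by the design.** With no participants affected out of 8, the one-sided 95% upper bound for the risk is 1 − 0.05^(1/8) = 0.31, however causality is defined.

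**The case against.** A reader might infer that an event is *Not related* whenever another factor can explain it, whatever the drug contributed, and that the treatment-related tables therefore cannot show a nemolizumab effect. The documents do not support that.

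- The *Not related* row opens with a judgement that a relationship is unlikely, and the call needs a written rationale. The *Related* row excludes only events that are readily explained.
- The footnote allows dechallenge, rechallenge and known drug effects to be weighed. It is permissive, but it is there.
- No passage forces an infection on permitted steroid to be called *Not related*. Whether the steroid explains the event is the investigator's decision.
- Section 17.3.3 1) tabulates numbers of participants and occurrences. Step 4 shows the related count rising with the rate ratio, and the related table is certain to be empty only at q = 1. The share of events called related stays constant there only because q was held fixed, which is an assumption.
- Every AE is recorded regardless of causality. The AESIs are tabulated by category and preferred term, and SAEs go to the sponsor within 24 hours whatever their label.

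All of this stands, and it limits the point to inconsistency and under-counting. It does not remove the overlap in Step 1. The footnote does not say how to class a mixed-cause event, and naming another factor satisfies the rationale requirement.

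A further objection is that a wider *Related* class would move the related table towards the all-causality table without separating drug effect from background. That is fair. Eight participants without a control arm cannot make that separation under either wording. The case for the change rests on consistent labels.

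**Conclusion.** The definitional fault holds. The rows overlap for plausibly timed events with a possible but not ready alternative explanation, and they are silent on contributory causation. Treatment-related AE counts and recorded SAE causality can therefore vary between investigators and be understated for events with common background causes.

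The size cannot be fixed from the documents, which give neither event rates nor the share of events with another explanation. In the illustration at p = 0.3, moving q from 0.25 to 0.75 cuts the expected related participants from 1.8 to 0.6. The conclusion about the rows does not depend on these numbers. The direction of the bias assumes that some events with another explanation also have a drug contribution and are classed by that explanation alone.

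The related tables are not necessarily empty, and no event is lost from the all-causality AE and AESI tables. This is a correction to a definition, with limited reach.

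**What to change.** Make the two rows of Table 11-1 complementary:

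- *Related*: the temporal relationship is plausible and there is a reasonable possibility that the product caused or contributed to the event, even if another factor may also have contributed.
- *Not related*: there is no plausible temporal relationship, or a contribution of the product is judged not reasonably possible, for example because another cause is established. The rationale is still required.

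State that the footnote considerations are to be applied to that judgement, align the CRF guidance, and use the revised classes for the treatment-related tables in section 17.3.3 1) and for SAE causality under section 11.5. State also that infections and the other AESIs will be read primarily from the all-causality AE and AESI tables.

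The cost is two sentences in the table and matching CRF guidance, with no new data. The downside is that treatment-related counts will be somewhat higher.
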